12.2. Definition of Adverse Events

12.2.1. Definition of Adverse Events

The following definitions from the International Conference on Harmonisation (ICH) Guideline E2A will apply to the reporting of AEs and adverse drug reactions:

Adverse Event: Any untoward medical occurrence in a patient or clinical investigation patient administered a pharmaceutical product and which does not necessarily have to have a causal relationship with this treatment.

Adverse Drug Reaction: All noxious and unintended responses to a medicinal product related to any dose.

The phrase, "responses to a medicinal product" means that a causal relationship between a medicinal product and an adverse event is at least a reasonable possibility, i.e., the relationship cannot be ruled out.

Unexpected Adverse Drug Reaction: An adverse reaction, the nature or severity of which is not consistent with the Investigator's Brochure.

Serious Adverse Event: Any untoward medical occurrence that at any dose:

- Results in death
- Is life-threatening
 - The term "life-threatening" refers to an event in which the patient was at risk of death at the time of the event; it does not refer to an event, which hypothetically might have caused death if it were more severe.
- Requires inpatient hospitalization or prolongs existing hospitalization

CONFIDENTIAL

No use, disclosure or reproduction outside of Omeros without prior written authorization

- Results in persistent or significant disability/incapacity
- Is a congenital anomaly/birth defect

Serious adverse events also include important medical events that may not be immediately life-threatening or result in death or hospitalization but may jeopardize the patient or may require intervention to prevent one of the other outcomes listed in the definition above. Examples of such events are intensive treatment in an emergency room or at home for allergic bronchospasm; blood dyscrasias or convulsions that do not result in hospitalization; or development of drug dependency or drug abuse.

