12.3. Reporting Adverse Events

12.3.1. Adverse Event Reporting

Adverse events will be collected from the time informed consent is obtained until the last Follow-up visit.

All AEs will be documented in the source records and will be recorded in the CRFs as appropriate. All AEs, whether observed by the Investigator or reported by the patient, and whether or not thought to be related to the study drug, will be recorded on the appropriate CRF. In describing AEs on the CRF, standard, medically accepted terminology will be used.

The description of each AE will identify the date of onset, duration, severity (see Section 12.2.2 for Definitions of Severity), any action taken (including any diagnostic procedures or laboratory tests performed and all treatments that were administered), the outcome of the event, and relationship to the study drug.

Any medical condition that is present at the time that the patient is screened should be considered as baseline and not recorded as an AE. However, if the medical condition increases in frequency or severity during or following administration of the study drug, it will be recorded as an AE on the appropriate CRF.

An AE is defined as any untoward medical occurrence in a patient administered a pharmaceutical product and which does not necessarily have to have a causal relationship with this treatment. Adverse events may be reported by the patient, discovered by the Investigator and Investigator's staff, or detected through physical examination, laboratory test, or other means.

Adverse events include:

- Any unfavorable and unintended sign, medical diagnosis, or symptom that occurs between the time of the first administration of study drug and the study duration required by the protocol.
- Any new undesirable medical experience or an unfavorable and unintended change of an existing condition that occurs between the time of the first administration of study drug and the study duration required by the protocol, whether or not considered related to study drug.
- Abnormal laboratory findings considered by the Investigator to be clinically significant, i.e., those that are unusual for the population being studied or individual patient.

Whenever possible, the Investigator should group signs or symptoms that constitute a single diagnosis into a single event term. For example, cough, rhinitis, and sneezing might be grouped together as *upper respiratory tract infection*.

CONFIDENTIAL

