13.2.9.2. Adverse Events

Adverse events collected during the study and significant AEs will be combined for analysis. They will be labeled as AEs for simplicity. Significant AEs are the AEs that occurred outside the protocol-specified reporting period and will be collected for the HSCT-TMA patients only. For reporting purposes, AEs will be divided into 2 categories:

- Those that occurred prior to the start of study treatment (pre-treatment events) and
- Those that occur or worsen in intensity after the start of study treatment (treatment-emergent adverse events).

Summary of AEs will include the non-serious AEs during the AE evaluation period and all reported serious AEs. The AE evaluation period is defined from the time of informed consent to 37 days after the last study drug administration.

All AEs will be classified by system organ class and preferred term using the Medical Dictionary for Regulatory Activities (MedDRA). An AE is considered treatment-related if the relationship to study drug is either probable or possible as assessed by the Investigator.

Patient incidence of the following AEs will be provided:

- Pre-treatment AEs by MedDRA System Organ Class (SOC), preferred term, dose, and disease
- Treatment-emergent AEs by MedDRA SOC, preferred term, dose, and disease

CONFIDENTIAL

No use, disclosure or reproduction outside of Omeros without prior written authorization

- Treatment-emergent AEs by MedDRA preferred term, dose, and disease
- Treatment-related AEs by MedDRA SOC, preferred term, dose, and disease
- Treatment-emergent AEs by MedDRA preferred term, maximum severity, dose, and disease
- AEs leading to study discontinuation by MedDRA SOC, preferred term, dose, and disease
- Treatment-emergent serious AEs (SAEs) by MedDRA SOC, preferred term, dose, and disease
- Treatment-related SAEs by MedDRA SOC, preferred term, dose, and disease
- AEs leading to death by MedDRA SOC, preferred term, dose, and disease

In addition, the following analyses will be performed:

- Treatment-emergent AEs and treatment-emergent SAEs during the AE evaluation period will be summarized separately for patients with and without ADA postdose.
- Treatment-emergent AEs that started or worsen in intensity after the AE evaluation period will be summarized with patient incidence by SOC, preferred term, disease group, and dose level.

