Significant Adverse Events	Each instance	Collect events (with dates) requiring hospitalization or intervention with medication or procedures.
Concomitant Medications		
All immunosuppressives and changes	Each instance at onset	Collect the dates of initiation and discontinuation with each dose per administration. Collect changes in the dose per administration and frequency with dates.
All anti-infectives and changes	Each instance at onset	Collect the dates of initiation and discontinuation.
All cytotoxics	Each instance at onset	Collect the dates of initiation and discontinuation.
All targeted therapies	Each instance at onset	Collect the dates of initiation and discontinuation.
All growth factors	Each instance at onset	Collect the dates of initiation and discontinuation.

CONFIDENTIAL

No use, disclosure or reproduction outside of Omeros without prior written authorization

Variables	Timing/Periodicity of Data Collection	Data Collection Rules/Definitions
Eculizumab	Each instance at onset	Collect the dates of initiation and discontinuation.
Defibrotide	Each instance at onset	Collect the dates of initiation and discontinuation.
Investigational agents	Each instance at onset	Collect the dates of initiation and discontinuation.
Total parenteral nutrition	Each instance at onset	Collect the dates of initiation and discontinuation.
Ursodeoxycholic acid	Each instance at onset	Collect the dates of initiation and discontinuation.
Heparin	Each instance at onset only for VOD prophylaxis	Collect the dates of initiation and discontinuation.
Laboratory Measures		
Platelet count	See laboratory measure schedule ¹	Collect from the clinical chart. Overlapping data will also be available from the central laboratory on some dates.
Hemoglobin	See laboratory measure schedule ¹	Collect from the clinical chart. Overlapping data will also be available from the central laboratory on some dates.
White blood cell	See laboratory measure schedule ¹	Collect from the clinical chart. Overlapping data will also be available from the central laboratory on some dates.
Absolute neutrophil count	See laboratory measure schedule ¹	Collect from the clinical chart. Overlapping data will also be available from the central laboratory on some dates.
Lactate dehydrogenase	See laboratory measure schedule ¹	Collect from the clinical chart. Overlapping data will also be available from the central laboratory on some dates.

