2. STATISTICAL METHODS

2.1. Study Endpoints

The co-primary endpoints are:

- Safety as assessed by adverse events (AE)s, vital signs, electrocardiograms (ECG)s, and clinical laboratory tests (includes patients with HSCT-TMA, aHUS, and TTP)
- For HSCT-TMA patients, response to OMS721 treatment. A responder is defined as a patient with HSCT-TMA who demonstrates improvement in laboratory TMA markers (platelet count and LDH) and clinical benefit (either improvement in organ function or reduction in transfusion burden). The specific criteria are defined as follows:
 - Improvement in laboratory TMA markers:
 - Platelet count:
 - For patients with baseline platelet count $\leq 20,000/\mu\text{L}$:
 - Tripling of baseline platelet count
and
 - Post-baseline platelet count $> 30,000/\mu\text{L}$
and
 - No platelet transfusions 2 days before and on the day of the platelet count collection
 - For patients with baseline platelet count $> 20,000/\mu\text{L}$
 - Increase in platelet count $\geq 50\%$
and
 - Post-baseline platelet count $> 75,000/\mu\text{L}$
and
 - No platelet transfusions 2 days before and on the day of the platelet count collection
 - and
 - LDH:
 - LDH < 1.5 x upper limit of normal (ULN)

and

- Improvement in clinical status:
 - Improvement in organ function as evidenced by any of the following:
 - Improvement in renal function:
 - Reduction of creatinine > 40%
 - or
 - Creatinine < ULN and reduction of creatinine > 20%
 - or
 - Discontinuation of renal replacement therapy (RRT),
 - or**
 - Improvement in pulmonary function:
 - Extubation and discontinuation of ventilator support
 - or
 - Discontinuation of non-invasive mechanical ventilation (continuous positive pressure ventilation)
 - or**
 - Improvement in neurological function:
 - Improvement in reversible neurological conditions (e.g., cessation of seizures)
 - or
 - Stabilization of irreversible neurological conditions (e.g., stability of neurological deficits following stroke without further deterioration or subsequent strokes)
 - or**
 - Improvement in gastrointestinal function (gastrointestinal HSCT-TMA will require diagnosis by tissue biopsy):
 - Improvement measured by improvement in the gastrointestinal measures in the Mount Sinai Acute GVHD International Consortium (MAGIC) criteria
 - or**

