3.4. Analysis of Safety Endpoints

3.4.1. Clinical Adverse Events

Adverse events collected during the study and significant AEs will be combined for analysis. They will be labeled as adverse events for simplicity. Significant AEs are the AEs that occurred outside the protocol-specified reporting period and will be collected for the HSCT-TMA patients only. For reporting purposes, AEs will be divided into 2 categories:

1. Those that occurred prior to the start of study treatment (pre-treatment events) and
2. Those that occur or worsen in intensity after the start of study treatment (treatment-emergent adverse events).

Summary of AEs will include the non-serious AEs during the AE evaluation period and all reported serious AEs. The AE evaluation period is defined from the time of informed consent to 37 days after the last study drug administration.

All AEs will be classified by system organ class and preferred term using the Medical Dictionary for Regulatory Activities (MedDRA). An AE is considered treatment related if the relationship to study drug is either probable or possible as assessed by the investigator.

Patient incidence of the following AEs will be provided:

- Pre-treatment AEs by MedDRA System Organ Class (SOC), preferred term, dose and disease
- Treatment-emergent AEs by MedDRA SOC, preferred term, dose and disease
- Treatment-emergent AEs by MedDRA preferred term, dose and disease
- Treatment-related AEs by MedDRA SOC, preferred term, dose and disease
- Treatment-emergent AEs by MedDRA preferred term, maximum severity, dose and disease
- AEs leading to study discontinuation by MedDRA SOC, preferred term, dose and disease
- Treatment-emergent serious AEs (SAEs) by MedDRA SOC, preferred term, dose and disease
- Treatment-related SAEs by MedDRA SOC, preferred term, dose and disease
- AEs leading to death by MedDRA SOC, preferred term, dose and disease

In addition, the following analyses will be performed:

- Treatment-emergent AEs and treatment-emergent SAEs during the AE evaluation period will be summarized separately for patients with and without anti-drug antibody postdose.
- Treatment-emergent AEs that started or worsen in intensity after the AE evaluation period will be summarized with patient incidence by SOC, preferred term, disease group and dose level.
- Pre-treatment and treatment-emergent significant infections will be summarized by infection type which will be determined before database lock and will be documented in the CSR.

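### Serious AE and fatal-AE tables by disease rest on unequal collection windows, because SAEs have no end date and late events are collected in HSCT-TMA only; add within-window tables and person-time.

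*SAP*

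**What the plan says.** Safety in HSCT-TMA, aHUS and TTP is a co-primary endpoint (protocol 7.3.1, SAP 2.1).

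**Counting rule.** SAP 3.4.1 and protocol 13.2.9.2 give the same rule: "Summary of AEs will include the non-serious AEs during the AE evaluation period and all reported serious AEs". They also define the period: "The AE evaluation period is defined from the time of informed consent to 37 days after the last study drug administration". Treatment-emergent means starting or worsening after treatment begins, with no end date.

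**Extra data for one disease.** "Significant AEs are the AEs that occurred outside the protocol-specified reporting period and will be collected for the HSCT-TMA patients only". They are not kept apart: "Adverse events collected during the study and significant AEs will be combined for analysis". Protocol 19.4, Table 2, says what is abstracted: "Collect events (with dates) requiring hospitalization or intervention with medication or procedures". The records run from transplant conditioning to last contact, or at most 104 weeks after first dose. Protocol 7.1 adds a data cutoff for patients who have not reached two years.

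**The other two diseases.** Only the ordinary rule in protocol 12.3.1 applies: "Adverse events will be collected from the time informed consent is obtained until the last Follow-up visit".

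**Tables.** Treatment-emergent SAEs and AEs leading to death are shown as patient incidence by dose and disease. No patient-time rate is specified. The plan also has a table of treatment-emergent AEs arising after the evaluation period by disease and dose, AE and SAE summaries within the period split by anti-drug antibody (ADA) status, and full listings.

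**The concern.** The main SAE and fatal-AE tables put the three diseases side by side under one label, but events are gathered for much longer in one of them. A patient observed longer has more opportunity to appear in a crude incidence table. In HSCT-TMA the added time also covers the later transplant course, well after a course of four or eight weekly doses. A reader could take a higher SAE percentage in HSCT-TMA for a difference in drug safety when part of it comes from a longer record search. The interim report built on these tables is meant to support a submission for approval (SAP 2.8.5).

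The pre-treatment AE table has the same asymmetry: HSCT-TMA events can reach back to conditioning, while those in aHUS and TTP start at consent.

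**Working it through.** **1. Windows.** Inputs are the visit days in protocol 7.1.1, 7.1.2 and 19.1 to 19.3. The maximum HSCT-TMA window is 104 × 7 = 728 days after first dose.

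| Group | Last dose (day) | Last follow-up (day) | Difference | 728 ÷ last follow-up day | Last dose + 37 |
|---|---|---|---|---|---|
| Stage 1 | 22 | 78 | 56 d = 8 wk | 9.3 | Day 59 |
| Cohort 5, Stage 2 only | 22 | 92 | 70 d = 10 wk | 7.9 | Day 59 |
| Cohort 5, Stages 2 and 3 | 50 | 92 | 42 d = 6 wk | 7.9 | Day 87 |
| aHUS, Stage 2 only | 78 | 120 | 42 d = 6 wk | 6.1 | Day 115 |
| aHUS, Stages 2 and 3 | 162 | 204 | 42 d = 6 wk | 3.6 | Day 199 |

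The differences reproduce the protocol's stated follow-up of 8, 10, 6, 6 and 6 weeks. Each last-dose-plus-37 day falls before the last follow-up visit, so within-window data are scheduled for every disease.

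**2. Where the contrast is cleanest.** SAP Table 1 has 4 TTP and 22 HSCT-TMA patients in Cohort 5 at 4.0 mg/kg on the same schedule. Their maximum windows are 92 and 728 days.

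**3. Do late events enter as serious?** The abstraction criterion includes hospitalization, and one SAE criterion in protocol 12.2.1 is "Requires inpatient hospitalization or prolongs existing hospitalization". The overlap makes entry likely for hospitalizations. It is an inference, because Table 2 does not say that seriousness is recorded. Significant AEs that needed only medication or a procedure need not be serious. If non-serious and late, they are excluded from the main summary.

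**4. Can the planned tables be undone?** Let A patients have any treatment-emergent SAE and B have a late one. The number with a within-window SAE lies anywhere from A − B to A, since one patient can have both. The late-event table is also not limited to serious events. The ADA-split SAE summary is within-window but not specified by dose or disease. The listings allow a hand count, which is not a planned analysis.

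**5. Illustration (assumed rates).** Use the same constant first-SAE rate r per week in every group, ignoring death and data cutoff. Incidence = 1 − exp(−r × weeks), with days rounded to whole weeks.

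| r | 13 wk (TTP, Day 92) | 17 wk (aHUS, Day 120) | 29 wk (aHUS, Day 204) | 104 wk (HSCT-TMA maximum) |
|---|---|---|---|---|
| 1% | 12.2% | 15.6% | 25.2% | 64.7% |
| 0.5% | 6.3% | 8.1% | 13.5% | 40.5% |

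If HSCT-TMA follow-up were only 52 weeks, the 1% rate gives 1 − exp(−0.52) = 40.5%.

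**6. Effect of a 37-day limit alone.** At 1% per week, Days 59, 87, 115 and 199 give 8%, 12%, 15% and 25%. TTP and HSCT-TMA then match at the same stage. aHUS still counts for longer because its treatment is longer, so person-time is needed as well.

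**The case against.** **No between-disease test is planned.** Safety is descriptive, and aHUS and TTP are summarized separately. This stands as a limit on the harm: no inference depends on the tables. It does not cure a co-primary safety display whose counting rule differs by disease.

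**The illustration overstates.** 104 weeks is a maximum, and death shortens it. Protocol 5.1.2.3 cites a series with 4 of 24 adults (17%) alive at one year. With first non-fatal SAE rate r and death rate m, incidence is r/(r+m) × [1 − exp(−(r+m) × 104)]. Take r = 0.01 per week. One-year survival of 17% gives m = −ln(0.17)/52 = 0.034 and incidence of about 22%. An assumed 50% survival gives m = 0.0133 and about 39%. This stands: 65% is an upper illustration. A longer window can still only add to the fatal-AE count.

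**Counting all SAEs is defensible.** Infection is a stated potential risk (protocol 10.2.1.5), and regulators asked for the long-term data. This stands, so the all-SAE tables should remain.

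**Stronger readings that a reader might infer, and that the documents do not support:**

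- *Every late hospitalization is a treatment-emergent SAE.* How seriousness is recorded for abstracted events is not stated.
- *The treatment-related SAE table is distorted too.* It needs an investigator rating of probable or possible, and Table 2 lists no causality item for significant AEs.
- *The 370 mg and 4.0 mg/kg columns in HSCT-TMA are also unequal to a degree that matters.* The 370 mg amendment is dated 12 Oct 2018, 598 days (85 weeks) before Amendment 11.1, but the data cutoff is not given and only 4 patients had 370 mg. At 1% per week, 57% against 65% is 0.08 × 4 = 0.3 of a patient.

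**Conclusion.** The concern holds in a limited form. Serious AEs have no end date, and events beyond ordinary reporting are added for one disease only. The maximum collection window in HSCT-TMA is 3.6 to 9.3 times that in the other groups, and 7.9 times that of TTP on the same Cohort 5 schedule. Crude treatment-emergent SAE and fatal-AE incidence by disease therefore mixes risk with length of collection, to the extent that late significant AEs are classed as serious.

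The size of the effect on the tables cannot be fixed from the documents. Actual follow-up, the data cutoff and the handling of seriousness are not given, and the percentages above are illustrations at assumed rates. TTP has only 4 patients at 4.0 mg/kg, so its column will be imprecise whatever the window; aHUS at that dose has 2 + 14 = 16.

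A reader might infer that the all-SAE tables should be replaced. The documents do not require that. The gap is the missing within-window SAE and fatal-AE tables by dose and disease, and the missing person-time.

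**What to change.** In SAP 3.4.1 and protocol 13.2.9.2:

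- Keep the tables of all reported SAEs and AEs leading to death, and label each disease column with its collection window.
- Add treatment-emergent SAE and AEs-leading-to-death tables by dose and disease, limited to first dose through last dose plus 37 days. State that any reading across diseases uses these.
- Give person-time, with events or patients per unit of patient-time, for the added tables and for the planned late-event table.
- State how seriousness is assigned to abstracted significant AEs.
- For pre-treatment AEs, tabulate events from informed consent by disease, and show earlier HSCT-TMA events separately.

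No event is dropped and no new data are collected for the added tables, which need a date filter and a patient-time denominator. The cost is a few more tables, to be read alongside the existing ones.

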1.2. Study Design

This is a Phase 2, uncontrolled, three-stage, ascending-dose-escalation study in patients with TMA: aHUS, TTP, or HSCT-TMA. As originally designed, the primary outcomes to be measured were safety and clinical activity. The secondary outcomes to be measured were PK, PD, and immunogenicity (i.e., presence of anti-drug antibody [ADA] response). Amendment [REDACTED] discontinued enrollment of patients with aHUS and TTP. Amendment [REDACTED] provides for collection of additional data from patients with HSCT-TMA, changes the primary and secondary objectives to focus on HSCT-TMA, and defines criteria by which to determine clinical response to treatment. Amendment 11 also provides for collection of PK and PD measures for analysis within integrated population PK and PD analyses across different studies.

In Stage 1 of the study, OMS721 was administered to 3 cohorts (Cohorts 1, 2, and 3), with dose escalation by cohort to identify the optimal dosing regimen. After enrollment and treatment of each cohort, there was a safety review to determine whether dose escalation should proceed. In Stage 2, the dose selected in the first stage was administered to expanded cohorts initially planned to be 40 patients per cohort with distinct etiologies (aHUS alone in 1 cohort, and TTP or HSCT-TMA in the other cohort). As of Amendment 10 of the protocol, enrollment of aHUS and TTP patients was closed.

Each patient in Stage 1 received 4 weekly doses of OMS721. Prior to Amendment 10, patients in Stage 2 with aHUS received 12 weekly doses and patients with TTP or HSCT-TMA received 4 weekly doses, and Stage 3 allowed for additional treatment based upon the patient's response to therapy. As of Amendment 11 of the protocol, Stage 1 is complete.

OMS721 will be administered by intravenous (IV) infusion. The planned enrollment is up to approximately 60 patients overall. The stages, cohorts, and treatments are provided in [Table 1](#).

Table 1: OMS721-TMA-001 Treatment Stages and Cohorts

Cohort and (Stage)	Number of Patients			OMS721 Dose
	aHUS	TTP	HSCT-TMA	
1 (Stage 1)	3	0	0	0.675 mg/kg weekly x 4
2 (Stage 1)	2	1	0	2.0 mg/kg weekly x 4
3 (Stage 1)	2	0	2	4.0 mg/kg weekly x 4
4 (aHUS only) (Stage 2 and 3)	14	0	0	4.0 mg/kg weekly x 12 for each Stage
	4	0	0	400 mg weekly x 12
5 (TTP or HSCT-TMA) (Stage 2 and 3)	0	4	22	4.0 mg/kg weekly x 4 for each Stage
5 (TTP or HSCT-TMA) (Stage 2 and 3)	0	0	4	370 mg weekly x 4 for each Stage

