aHUS = atypical hemolytic uremic syndrome; HSCT-TMA = hematopoietic stem cell transplant-associated thrombotic microangiopathy; TTP = thrombotic thrombocytopenic purpura

For patients with HSCT-TMA enrolled under Amendment [REDACTED] or under earlier versions of this protocol, additional data will be collected. Notification and consent of patients (or legal representatives for deceased patients) for this additional data collection will be performed as needed according to local rules and regulations.

These additional data are outlined in Protocol Amendment [REDACTED]. These data will include supplemental data on patient demographics and baseline conditions, donor characteristics, the transplant procedure, concomitant medications, TMA-related laboratory measures, transfusions, transplant complications, and outcomes. Details of these data are provided in Appendix 1 of the protocol amendment. These data will be derived from medical records from the time of transplant conditioning through the last available patient contact with the site or 2 years (104 weeks) after the first OMS721 dose, whichever is earlier. These data were requested by regulatory authorities because patients who have undergone HSCT typically have complicated post-transplant courses and these additional data will allow for better understanding of OMS721 response and outcomes. As of Amendment 11, enrollment in the study has been completed, and the additional data will be collected until a predetermined data cutoff date for those patients who have not reached 2 years after first OMS721 dose.

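### In aHUS, adverse events are tabulated by dose as crude patient incidence although course length rises with dose, so an apparent dose trend can arise with no dose effect

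*SAP*

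**What the plan says.** Safety is one of the two co-primary endpoints (SAP 2.1), and all safety analyses are descriptive (SAP 2.8.4).

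SAP 3.4.1 sets the measure: "Patient incidence of the following AEs will be provided". The main tables are of the form "Treatment-emergent AEs by MedDRA SOC, preferred term, dose and disease". On what is counted: "Summary of AEs will include the non-serious AEs during the AE evaluation period and all reported serious AEs". Protocol 13.2.9.2 defines the window: "The AE evaluation period is defined from the time of informed consent to 37 days after the last study drug administration".

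SAP 1.2, Table 1, gives the courses for aHUS:

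- Cohort 1, 3 patients: "0.675 mg/kg weekly x 4".
- Cohort 2, 2 patients: "2.0 mg/kg weekly x 4".
- Cohort 3, 2 patients: 4.0 mg/kg for 4 doses.
- Cohort 4, 14 patients: "4.0 mg/kg weekly x 12 for each Stage", in Stages 2 and 3.
- Cohort 4, a further 4 patients: 400 mg for 12 doses.

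SAP 3.2.2.2 summarizes number of doses and duration of treatment by dose and disease, apart from the AE tables. Neither document plans an exposure-adjusted AE rate, a common time window, a time-to-first-event analysis of AEs, or a split of the 4.0 mg/kg aHUS patients by course length.

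**The concern.** Crude incidence counts a patient once if the event occurs at any time in the window. Patients watched longer have more chance to be counted. Within aHUS the two lowest doses have only the shortest window and the 4.0 mg/kg column is mostly longer windows, so dose and observation time are nearly inseparable in adjacent columns of the same table.

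A reader of the aHUS panel could take a rise in AE incidence from 0.675 or 2.0 to 4.0 mg/kg as dose-related toxicity when it reflects longer observation. Equally, a real dose effect could not be told apart from the artefact. This matters because safety is co-primary and the report is meant to support a regulatory submission (SAP 2.8.5).

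**Working it through.** **Inputs.** Patient numbers and courses: SAP Table 1. Weekly dosing from Day 1 and follow-up days: Protocol 7.1.2, 10.1.1, 19.1 and 19.2. The 37-day tail: SAP 3.4.1 and Protocol 13.2.9.2.

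**Schedule.** Last dose day = 7 × (doses − 1) + 1. This gives Day 22 for 4 doses, Day 78 for 12 and Day 162 for 24, matching the Schedules of Events.

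**Non-serious AE window from first dose**, for a completed course = last dose day + 37:

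- 4 doses: 22 + 37 = 59 days
- 12 doses: 78 + 37 = 115 days (1.95 times)
- 24 doses: 162 + 37 = 199 days (3.37 times)

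**Scheduled AE and SAE collection** in aHUS ends at the last follow-up visit: Day 78 (Stage 1), Day 120 (Stage 2 only) or Day 204 (Stage 3). The ratios are 120/78 = 1.54 and 204/78 = 2.62.

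**Illustration with no dose effect.** Assume the same constant hazard at every dose. The documents give no event rate, so p, the incidence over 59 days, is varied. Incidence over T days = 1 − (1 − p)^(T/59). The pooled 4.0 mg/kg column is (2 × p + 14 × long-course incidence)/16. Stage 3 uptake is not given, so the two extremes are shown.

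| p (4 doses) | 12 doses | 24 doses | 4.0 mg/kg column, all 14 on 12 | 4.0 mg/kg column, all 14 on 24 |
|---|---|---|---|---|
| 5% | 9.5% | 15.9% | 9.0% | 14.5% |
| 10% | 18.6% | 29.9% | 17.5% | 27.4% |
| 20% | 35.3% | 52.9% | 33.4% | 48.8% |
| 30% | 50.1% | 70.0% | 47.6% | 65.0% |
| 50% | 74.1% | 90.3% | 71.1% | 85.3% |

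For p = 20%: (2 × 20 + 14 × 35.3)/16 = 33.4, and (2 × 20 + 14 × 52.9)/16 = 48.8.

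**SAEs, same assumption, scheduled collection.** A 20% incidence by Day 78 becomes 1 − 0.8^1.54 = 29.1% by Day 120 and 1 − 0.8^2.62 = 44.2% by Day 204. The pooled column is (40 + 14 × 29.1)/16 = 28.0% to (40 + 14 × 44.2)/16 = 41.2%.

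**Imprecision.** In a simulation with p = 20%, the 16 patients at 4.0 mg/kg show higher crude incidence than the 5 low-dose patients with probability 72% (all 14 on 12 doses) to 90% (all on 24). With equal windows it is 49%.

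**Does a rate remove it?** Under the same assumption, first events per patient-year = −ln(0.8)/59 × 365.25 = 1.38 for all three course lengths.

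**Other diseases.** In TTP, 1 patient had 2.0 mg/kg for 4 doses and 4 had 4.0 mg/kg for 4 doses per stage: 59 days against at most 50 + 37 = 87. In HSCT-TMA, the Cohort 5 patients at 4.0 mg/kg (22) and 370 mg (4) share the same planned course of 4 doses per stage.

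**The case against.** The strongest reply is that nothing turns on this contrast. The plan tests no dose difference in AEs. The low-dose aHUS columns hold 3 and 2 patients, aHUS enrollment is closed, and the efficacy analyses focus on HSCT-TMA. Duration of treatment is tabulated, all AEs are listed, and AEs starting after the evaluation period get their own by-dose table, so an attentive reader can see that exposure differed. All of this stands and limits the weight of the point. It does not remove the bias: a separate duration table shows that windows differ without correcting the incidence beside it.

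Four stronger readings are tempting, and the documents do not support them.

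- *These are the trial's only dose-safety comparison.* They are not. Stage 1 reviewed three doses on equal 4-dose courses and used that review in choosing the dose (Protocol 10.4.1). Laboratory tests, vital signs and ECGs are also tabulated by dose.
- *The tables will show more toxicity at 4.0 mg/kg.* This holds only in expectation under an assumed constant hazard. Events concentrated early, such as infusion reactions, would be inflated less.
- *The 3.4-fold spread applies to SAEs.* Scheduled collection in aHUS spreads 2.6-fold. Chart-collected significant AEs outside the reporting period apply to HSCT-TMA only.
- *370 mg will show fewer SAEs in HSCT-TMA because follow-up is shorter.* SAP 1.2 says only that "the additional data will be collected until a predetermined data cutoff date for those patients who have not reached 2 years after first OMS721 dose". The cutoff date and the patients' survival are not given, there are 4 patients, and unequal follow-up could be small or run either way.

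**Conclusion.** The point holds for the aHUS stratum. The by-dose AE tables set 59-day windows beside windows of 115 to 199 days, and no planned analysis puts them on a common footing. For an AE with 20% incidence at the low doses, the pooled 4.0 mg/kg column would be expected to show about 33% to 49% with no dose effect. The 400 mg column, on 12 doses, would show about 35%. These figures assume a constant hazard, completed courses and a chosen event rate. The window lengths depend only on the schedule and completion of the course.

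The effect is a tendency in a descriptive table with 3, 2 and 16 patients, so any trend seen there is very imprecise. TTP is affected less. In HSCT-TMA the concern is limited to possibly unequal SAE follow-up, whose size and direction cannot be established from the documents. The correction is worth making because safety is co-primary and the change is cheap.

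**What to change.** In SAP 3.4.1 and Protocol 13.2.9.2, keep the planned tables and add two summaries by dose and disease:

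1. Patient incidence of treatment-emergent AEs and SAEs from Day 1 to Day 28. Every cohort is then on the same weekly schedule with four planned doses, and no one has entered Stage 3. A Day 1 to 59 window would equalize observation time, but low-dose patients would be off drug while Cohort 4 was still being treated.
2. AEs per unit of patient-time over the AE evaluation period, and SAEs per unit of patient-time of actual follow-up. Add a note that Stage 3 entry depended on response and tolerability (Protocol 7.1 and 7.4), so rates beyond Stage 2 come from selected patients.

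State that any reading of AEs across doses uses these two tables.

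The cost is SAP and protocol wording and a few tables from data already collected. The drawbacks are small numbers in the 28-day window and the loss of later events from that table. The patient-time rates and the planned tables still carry those events.
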